not meeting one or more evidence-based primary care management outcomes related to preventive screening [e.g. cancer screening], disease management [i.e. risk factor testing or control], or medication taking [evidence of non-adherence based on pharmacy dispensing or self-report]). In these Step 1 interviews, we focus on understanding whether and how patients prepare for upcoming visits and how they conceptualize the relative importance of different health issues. For each participant, we also elicit a specific list of their current health care priorities that they want to discuss with their physician. With each patient's prior consent, in Step 2 we interview each participant's physician. In the Step 2 interviews we elicit the physician's priorities for the patient, compare the physician and patient listed priorities, and investigate how each physician would seek to balance any differences between the two sets of priorities. Finally, in Step 3 we close the loop by returning to the patient. In the Step 3 interviews, we present patients with physician priorities and investigate how the patient perceives any differences between his/her priorities and PCPs.

Aim 2 is the IT development of the tablet application and does not involve human subjects.

Aim 3 Clinical Trial

We conducted a 2-arm parallel group clinical trial with random, concealed allocation at the level of PCP. Both PCPs and patients provided informed written consent. Patients, providers, and waiting room research assistants cannot be blinded to randomization status because treatment patients are given the Visit Planner tool in the waiting room while control patients are not. However, collection of post-visit survey data and assembly of analytic datasets is masked to randomization status. For **Aim 3**, we enroll PCPs and their patients from KPNC primary care practices in Oakland and San Francisco. PCPs are recruited via their weekly practice meetings and through individual in-person contacts.

Intervention

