- a. If you will obtain surrogate consent, describe detailed research plan to the surrogate, including present and future decisions to be made. A documented assessment of decisional capacity as part of the procedures for obtaining surrogate consent should be included.

N/A

Other Populations Targeted for Recruitment

N/A

d. Setting

The clinical trial was conducted within KPNC primary care practices located at Oakland and San Francisco – Mission Bay. Study procedures were conducted by research personnel.

e. Recruitment Methods

On 1/22/16, the IRB approved the “Aligning Patient and Providers” clinical trial. Intervention arm patients have the opportunity to use the Align Waiting Room Tool (an iPad based application that helps them prepare for their visit) while control patients receive a KP-designed handout on healthy lifestyle advice.

We have the following research protocol for our clinical trial:

- 1) As with our procedure for our similar ongoing clinical trial (CN-13-1579 – Pre-Visit Prioritization for Complex Patients with Diabetes), [name] contacts Primary Care Practice Leaders (via e-mail or in-person) to request permission to present the “Aligning Patient and Providers” clinical trial at a weekly practice meeting. At this meeting, [name] explains the purpose for his visit, describes the study, and identifies providers willing to participate. With help from research staff, [name] then obtains written informed consent from willing physicians. Consenting physicians also review a list of their own potentially eligible patients to approve contacts and complete the 5-item baseline questionnaire at this time. This entire process takes 20-30 minutes.
- 2) PCP-approved patients are then sent a letter explaining the study. The letter includes a phone number and e-mail address for patients who wish to participate or opt out of the study. After 1 week, we contact patients who have not yet responded and – using our phone script – invite patients to participate in our study.

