- 3) We obtain verbal informed consent during this phone call to administer a brief patient baseline questionnaire and arrange with patients to meet ahead of time at their primary care practice on the day of their next scheduled visit. For visits that occur > 1 week after the initial phone enrollment, we also make a reminder phone call. Our team has previously created an informatics tool that alerts us when study participants have scheduled an appointment with their primary care physician.
- 4) At the primary care practice prior to their visit, the research assistant obtains written informed consent. Patients allocated to the intervention arm are then given the pre-loaded iPad with the Visit Planner Waiting Room Tool that helps them prepare for their visit. This tool takes approximately 4 minutes to complete. On completion of the program, the research assistant prints out the patient’s answers and the patient can bring this page into the exam room to remind themselves of their visit priorities and plans. As is clearly explained to the patient, none of the answers entered by the patient become part of the medical record and are only for the patient’s own use. Control patients receive the “Healthy Living/Physical Activity - Every Move Matters” KP-designed 2-page pamphlet.
- 5) Patients are called within 2 days after their visit at a previously arranged time and asked to complete the post-visit survey. All patients completing these surveys receive a \$20 gift card mailed to their home.

f. Informed Consent Process

The study investigator or project manager reviews and presents the consent form before the scheduled interview in the waiting room. We ask if the individual has any questions, provide answers, and obtain signed informed consent prior to the interview beginning.

We do not enroll participants if they cannot provide informed consent due to severe cognitive impairment, language issues, or other incapacity. We screen for these issues during the recruitment telephone call. However, any issues of this nature not evident during that call and noted during the consenting process are handled on a case by case basis by the person obtaining informed consent.

Waiver of Informed Consent

N/A

Waiver of Signed Informed Consent

N/A

Alteration of Informed Consent

N/A

Non-English-Speaking Subjects

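### Allocation is concealed at PCP level only and, under step 4, unblinded staff take patients' written consent at the visit, so selection at entry could differ by arm; the plan has no check for it

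*Combined protocol and SAP*

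**What the plan says.** Section 3 (Aim 3 Clinical Trial) describes "random, concealed allocation at the level of PCP" and states that "Patients, providers, and waiting room research assistants cannot be blinded to randomization status". Its masking claim follows: "However, collection of post-visit survey data and assembly of analytic datasets is masked to randomization status". Recruitment is not mentioned there.

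Section 4e gives the order of entry:

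- Step 1: PCPs consent at a practice meeting. "Consenting physicians also review a list of their own potentially eligible patients to approve contacts".
- Step 2: approved patients get a letter. "After 1 week, we contact patients who have not yet responded and – using our phone script – invite patients to participate in our study".
- Step 3: verbal consent and a brief baseline questionnaire are taken by phone.
- Step 4: "At the primary care practice prior to their visit, the research assistant obtains written informed consent". The tool or the handout is then given. No patient-level randomisation step is described.

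Section 4f says instead that the investigator or project manager presents the consent form in the waiting room. It leaves capacity problems that surface at that point to the case-by-case judgement of whoever is taking consent.

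The models in section 5a contain arm as a fixed effect and PCP as a random effect. No patient covariate is named. Baseline characteristics are to be compared by arm, with no stated consequence if they differ. Section 4b keeps information on decliners so that they are not contacted again; no recruitment counts by arm are planned.

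**The concern.** Randomising PCPs balances PCPs and, in expectation, their whole panels. It does not balance the patients who enter after the arm is known to those recruiting them. If staff persist more with some patients in one arm, or if different kinds of patient agree, the enrolled groups can differ even though the panels do not. More engaged patients are plausibly more likely to close care gaps (H2) and to report good communication (H1), so an arm enriched with them could look better with no effect of the tool.

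The stated protections do not reach this. Masked survey collection and dataset assembly come after entry. The PCP random effect handles correlation within PCP, but a selection difference that runs along the arm contrast goes straight into the arm coefficient.

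**Working it through.** **Order of events.** The plan states no figure on this point, so there is nothing to reproduce. The check is what each section fixes.

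| Step | Does the person acting know the arm? |
|---|---|
| PCP approves list (4e step 1) | Not stated; done when the PCP consents, possibly before allocation |
| Letter, call, phone consent (4e steps 2-3) | Not stated; neither the timing of PCP randomisation nor caller masking is given |
| Written consent (4e step 4) | Research assistant: yes, from the PCP's second study visit at the latest |
| Written consent (4f) | Investigator or project manager: not stated |
| Post-visit survey, datasets (section 3) | Masked |

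**Share of written consents given after the PCP's arm is in use.** With K PCPs each enrolling at least one of the 750 patients (section 4a), the share is 1 - K/750.

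- K = 300: 1 - 300/750 = 450/750 = 60%. Section 2b counts just over 300 PCPs at three centres; the trial used two sites, so K = 300 is generous and about 60% is near a floor.
- K = 150 (5 patients per PCP): 80%.
- K = 75 (10 per PCP): 90%.

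These shares concern visit-day consent. They say nothing about phone invitation.

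**Illustrative size.** Every input here except 750 is assumed: 375 per arm; no true effect; half of candidates engaged and half less engaged; 60% consent in both types in control; consent a (engaged) and b (less engaged) in intervention; outcome rates h and l in the two types; selection acting on a fraction f of intervention patients.

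- Engaged share where selection acts: s = a/(a + b).
- Spurious difference: D = f × (s - 0.5) × (h - l).
- SE = √[pC(1 - pC)/375 + pT(1 - pT)/375], with pC = (h + l)/2 and pT = pC + D.
- Rejection rate = Φ(D/SE - 1.96) + Φ(-D/SE - 1.96).

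Example, closure with h = 50%, l = 30%, a/b = 80/40, f = 1: s = 80/120 = 0.667; D = 0.167 × 0.20 = 0.033; SE = √(0.40 × 0.60/375 + 0.433 × 0.567/375) = 0.036; D/SE = 0.93; rate = 15%.

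Each cell gives the spurious difference in points and the rejection rate at nominal 5%. The survey item has h = 80%, l = 50%.

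| a/b | Closure, f = 1 | Closure, f = 0.6 | Survey, f = 1 | Survey, f = 0.6 |
|---|---|---|---|---|
| 65/55 | 0.8; 5.6% | 0.5; 5.2% | 1.25; 6.5% | 0.75; 5.5% |
| 70/50 | 1.7; 7.5% | 1.0; 5.9% | 2.5; 11% | 1.5; 7.2% |
| 80/40 | 3.3; 15% | 2.0; 8.6% | 5.0; 31% | 3.0; 14% |

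f = 1 lets selection act on everyone; f = 0.6 restricts it to the 60% share above.

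**Clustering.** With an assumed ICC of 0.03 and 10 patients per PCP, the design effect is 1 + 9 × 0.03 = 1.27. Replacing 375 by 375/1.27 lowers the f = 1 closure rates to 5.5%, 7.0% and 13%, and the largest survey rate to about 25%. The spurious difference is unchanged; it is only set against more noise.

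**The case against.** The strongest reply is that little here shows recruitment going wrong. Candidates come from electronic algorithms (4b). One letter and one phone script are described, with no variation by arm. Lists are approved when the PCP consents. Patients in both arms are met in the waiting room, and all survey completers receive the same gift card. The baseline questionnaire is taken by phone before the visit, and baseline characteristics are compared by arm. Several of a PCP's patients could have been invited and phone-consented before that PCP's first study visit. Section 4f also leaves open whether the consent-taker is one of those listed as impossible to blind.

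Most of this stands, and it limits the point. A reader might infer that patients were invited after allocation, with the PCP's name giving the arm away on the phone. The documents do not support that: they are silent on both timing and caller masking. Nor is the person taking consent unambiguously unblinded, given the conflict between 4e step 4 and 4f. The larger error rates also need consent differences, such as 80/40 against 60/60, that have no basis in the documents.

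It does not dispose of the matter. Algorithms settle who may be approached, not who enrols. A script fixes the words of a call, not persistence or the waiting-room conversation. A baseline comparison with no consequence attached changes nothing in the analysis.

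**Conclusion.** The point holds as a gap in the plan. Under step 4, the last gate into the trial is run by staff who know the PCP's arm for at least about 60% of patients if no more than about 300 PCPs took part. Neither the masking claim nor the model covers selection there. Whether earlier steps were exposed cannot be told from the documents.

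Bias is possible, not shown. On the assumed inputs, the mildest consent difference leaves the error rate at about 5-6%. The largest gives about 9-15% for closure and about 14-31% for a survey item. These are illustrations, not estimates of this trial's error rate, and should not be read as evidence that the trial was biased. What matters is that the plan has no means of telling which case occurred, and a cheap analysis could help to show it.

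**What to change.** The last visit was on 6/30/17 and follow-up ended on 12/31/2017 (section 5), before this version (7/12/18). The remedy is therefore analysis and reporting.

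1. In section 5a, add a version of the H1 and H2 GLIMMIX models adjusted for patient characteristics fixed before the visit and already collected, for example baseline care-gap count, chronic conditions, age and language. Label it as a sensitivity analysis. Compare it with the main model on the risk-difference scale, since adjusted odds ratios can move without any imbalance.
2. Report by arm, as far as retained records allow, the numbers PCP-approved, invited, phone-consented and written-consented, and interpret the main result in that light.
3. State when PCPs were randomised relative to list approval, letters and calls, and whether callers were masked.
4. Reconcile 4e step 4 with 4f on who takes written consent.

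The cost is one further set of models, one flow table and a few sentences. There are limits: the contents of the decliner records and of the baseline questionnaire are not described, and adjustment cannot remove imbalance in engagement that was not measured.

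Masking the recruitment calls would apply only if recruitment were still open. It would also need written consent to be taken before the arm is revealed, or by someone unaware of it; otherwise the step 4 gap remains.

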Intervention patients are provided the Visit Planner on a tablet tool in the waiting room. The tool starts off with a video that explained the purpose of the application and educated patients about the importance of bringing up their concerns early rather than later in the visit. Then, the tool prompts them to choose their top 1 or 2 concerns for the visit from 6 categories (New Problem, Medicines, Need something from the doctor, Old Problem, Stress at home or at work, A personal concern or other). Within each category, patients have the option of choosing 3-4 sub-categories and of inputting additional comments in a free-text field. After identifying their top visit priorities, patients are then prompted to identify how they would use their time during or after the visit to stay involved with their care (e.g., Take notes during the visit, Ask my doctor questions during the visit, Review with a friend or loved one, Check online patient portal after the visit). All patient responses are subsequently printed out as a Visit Planner Summary for the patient to bring into their visit.

Control

Control patients are also met in the waiting room before eligible visits. Control patients are given a 1-page healthy lifestyle education handout.

Patients in both study arms otherwise receive usual care throughout the clinical trial period.

4. Study Population

a. Number of Subjects

Aim 3 clinical trial = 750 patients (modified)

b. Inclusion and Exclusion Criteria

PCP Eligibility: Providers are eligible for inclusion if they have at least 5 potentially study-eligible patients within their patient panel and plan to remain at their current practice for the following year.

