Patient Eligibility: We use the KPNC electronic clinical data repository to identify a broad spectrum of potentially eligible patients within each participating PCP's patient panel. Patient eligibility is defined as having **2 or more chronic conditions** (defined using our validated clinical data algorithms for the following common chronic conditions: type 2 diabetes, hypertension, cardiovascular disease, dyslipidemia, chronic obstructive pulmonary disease/asthma, depression, renal insufficiency, cancer, and symptomatic arthritis) and **1 or more Quantitative Clinical Care gaps** defined using KPNC-implemented quality metric algorithms (e.g. preventive cancer screening for breast, cervical, and/or colorectal cancer screening among screen-eligible patients; and to chronic disease management including annual HbA1c testing and **result < 8.0%** for patients with diabetes; annual blood pressure measurement and systolic blood pressure (SBP) < 140 mg Hg for patients with diabetes, hypertension, or cardiovascular disease (CVD); annual cholesterol measurement and LDL < 100 mg/dL for patients with diabetes or CVD). We exclude patients with psychosis or dementia or other deficits that significantly impair communication or use of computers. Screening is conducted via electronic record review and patient phone calls. We retain information from decliners so that subjects are not re-contacted after declining.

c. Vulnerable Populations

We do not make any special effort to include or exclude vulnerable populations, however our study only includes adult members with at least two complex conditions who can participate in an English or Spanish language interview. Each subject, including those in a vulnerable population listed above who may be randomly selected into our study sample, have the opportunity to decline participation and avoid further contact by study staff by returning the mailed reply postcard or by phoning the study coordinator. Given the very low-risk nature of study participation, i.e. survey completion on a PC tablet or interview participation, no additional safeguards, beyond standard confidentiality safeguards, are employed. TPMG physicians are assured that no individual identifiable responses gathered during interviews will be shared with others outside of the study team.

Decisionally Impaired Adults

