1. Securing storage of physical data (e.g., papers) in locked files, and securing storage of digital data (computer files, digital audio) in password-protected files on password protected computers.
2. Making data that may contain identifying features accessible only to members of the research team working under the direction of the investigators during the duration of the project.
3. Use of a study ID on all audio files and transcripts. The transcriptionist do not transcribe any identifying information. Study staff review hard copy transcripts and remove any remaining identifying information (such as names, place names, etc.). All audio files are destroyed after transcription.
4. Ensuring that no data are collected or maintained by investigators which participants do not want to have preserved.
5. Ensuring no participant can be identified in any presentations or publications about this study.
6. All study staff rated current in HIPAA and IRB training.

All drugs and devices used in the research and the purpose of their use, and their regulatory approval status. NA
The source records that will be used to collect data about subjects. Data are collected from the medical record and via patient and provider surveys.

What data will be collected including long-term follow-up. Long-term follow-up is based on data from the medical record collected as part of routine care.

The duration of an individual subject's participation in the study. Physicians were recruited at monthly physician meetings where the study was presented. The first eligible patient visit occurred on 3/31/2016 while the last visit occurred on 6/30/17.

The duration anticipated to enroll all study subjects. Enrollment of physicians began 2/2016 and was completed by 2/2017. Follow-up was assessed through 12/31/2017— 6 months after the final visit. We chose a 6-month follow-up period to balance factors of providing sufficient time for the intervention to make an impact while also reducing loss to follow-up.

a. Data Analysis

Study outcomes

Our primary clinical outcome is the closing of quality care gaps within 6 months of study visits. Individual care gaps are measured at baseline and 6-month follow-up as a total count of any care gap at both time periods. Change in aggregated care gaps from baseline to follow-up is also assessed in four ways: closure of all baseline gaps, closure of any baseline gaps, opening of new care gaps, and presence of no gaps at the end of the study.

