Our primary patient-reported outcomes regarding their care experiences are obtained during post-visit telephone calls using questions drawn from validated survey instruments. Surveys are conducted within 1 week of the eligible primary care visit. We measure outcomes in the domains of patient satisfaction, autonomy, perceived involvement in care, and satisfaction with care.²⁹⁻³⁴ Modeled on the structure of these validated items, we also add several study-specific questions to obtain more detailed information about bringing up top concerns at the beginning of the visit, taking notes and asking questions during the visit, and following up post-visit with friends

and loved ones. Finally, we examine responses to a 5-item PCP survey administered at baseline during study enrollment.

Statistical Methods

We examine baseline characteristics of patients and providers by randomization status using chi-square, t-test, and non-parametric tests as appropriate. For our clinical trial outcomes, we construct generalized linear mixed models (SAS Proc GLIMMIX) with the dichotomized response as a dependent variable (with a logit link), treatment/control arm as a fixed effect and PCP as a random effect to adjust for clustering of patients within PCP. For secondary survey outcomes, the patient reports are dichotomized and analyzed in the same type of mixed models. We also conduct a priori analyses of English vs. Spanish-speaking patients in sub-analyses to determine any differential effects by language. We use SAS version 9.3, SAS Institute, Cary NC.

b. Sharing of Results with Subjects

Results will not be directly shared with patients.

c. Data and/or Specimen Banking

NA

6. Privacy, Confidentiality and Data Security

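### The model for opening of new care gaps ignores how many metrics each patient could still fail; the test stays valid but gives up a little power

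*Combined protocol and SAP*

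**What the plan says.** Section 5a (Study outcomes) names the closing of care gaps within 6 months as the primary clinical outcome. It then adds four assessments of change. Two concern closure of the gaps present at entry (every one, or at least one), one is "opening of new care gaps", and one is having none when the study ends. It does not define a new gap, say which patients or metrics are at risk of one, or give an expected event rate.

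Section 5a (Statistical Methods) gives one model for the trial outcomes: "we construct generalized linear mixed models (SAS Proc GLIMMIX) with the dichotomized response as a dependent variable (with a logit link", with "treatment/control arm as a fixed effect and PCP as a random effect to adjust for clustering of patients within PCP". No other covariate, offset or restricted analysis set is named.

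Section 4b (Patient Eligibility) makes the metrics conditional on the patient. The examples include "preventive cancer screening for breast, cervical, and/or colorectal cancer screening among screen-eligible patients" and "annual cholesterol measurement and LDL < 100 mg/dL for patients with diabetes or CVD". HbA1c applies in diabetes, and blood pressure in diabetes, hypertension or CVD. Depression, COPD/asthma, renal insufficiency, cancer and arthritis count towards eligibility, but no disease metric is listed for them. At least one open gap is required for entry.

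Section 3 describes a "2-arm parallel group clinical trial with random, concealed allocation at the level of PCP", and section 4a gives 750 patients. No power, ICC or number of PCPs is stated.

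**The concern.** At baseline, a patient can open a new gap only on a metric that applies and is currently met. That number differs between patients and is a strong predictor of the outcome, yet it is not in the model. A patient with no such metric is recorded as having no new gap, which is the favourable result, whatever care is given.

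At stake is sensitivity on an outcome whose event is a deterioration in care. A tool that directs the visit to one or two patient-chosen concerns could plausibly displace routine testing, and this outcome is one place where that would show. The crude event percentage is also hard to read without knowing how many patients could have had the event.

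**Working it through.** There is no planned calculation to reproduce. Every rate below is an assumption.

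**1. Range of metrics at risk.** Counting testing and control separately, the section 4b examples give 3 (cancer screens) + 2 (HbA1c) + 2 (blood pressure) + 2 (cholesterol) = 9.
- Diabetic woman eligible for all three screens, one open gap: 9 − 1 = 8 at risk.
- Man with depression and arthritis, enrolled on an overdue colorectal screen: 1 − 1 = 0 at risk.

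Simulated populations built on these nine metrics (diabetes 25–60%, hypertension 50–80%, CVD 10–20%, baseline gap 25–35% per applicable metric) had 2–11% of patients with none at risk.

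**2. Effect of the patients with none at risk, taken alone.** Let f be their share and p the mean event rate among the others. The efficiency of analysing everyone, relative to at-risk patients only, is about (1 − p)/(1 − p(1 − f)). Take rates of 20% vs 12%, so p = 0.16, 375 per arm, two-sided 0.05, no clustering:
- f = 0.10: 0.84/0.856 = 0.981; power 0.803 (all) vs 0.811 (at risk).
- f = 0.20: 0.84/0.872 = 0.963; power 0.747 vs 0.763. The odds ratio moves from 0.545 to 0.558. The risk difference shrinks from 0.080 to 0.080 × 0.80 = 0.064.

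At shares like those in step 1 this component is small.

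**3. Adding the count.** Simulation: 750 patients, nine metrics, odds ratio 0.65 per metric, ordinary logistic regression, 70% screen-eligible. The stated model is compared with at-risk patients adjusted for the count, using z = |ln OR|/SE:
- Baseline gap 35%, new-gap risk 8%: 0.434/0.196 = 2.21 against 0.472/0.205 = 2.30. Relative efficiency (2.30/2.21)² ≈ 1.08.
- Baseline gap 30%, new-gap risk 12%: 0.462/0.161 = 2.87 against 0.512/0.170 = 3.01. Relative efficiency ≈ 1.10.

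The standard error rises in both cases (0.196 to 0.205; 0.161 to 0.170). Power improves because the odds ratio moves further from 1 (0.648 to 0.624; 0.630 to 0.599). Over a wider set of assumptions the relative efficiency was 1.05–1.16.

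**4. Clustering and unequal risks.** Step 3 gives every metric the same independent risk, which flatters the count as a covariate. With a PCP effect and unequal risks per metric, relative efficiency was about 1.05–1.09, or about 0–3 power points. Keeping all patients and adding the count retained 1.05–1.08; restriction alone gave 1.01–1.03.

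**5. Where the gain disappears.** If everyone has 2–4 metrics at risk, the gain is 1–3%. Adjusting for the number of gaps open at baseline instead gave 1.00, so that covariate is no substitute.

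**6. Validity.** With no true effect, the unadjusted analysis rejected in 0.044–0.070 of runs (800 per scenario, unclustered, Monte Carlo SE about 0.008), which shows no clear inflation.

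**The case against.** The best defence is that nothing is broken. Allocation is random, patients unable to open a gap are expected equally in both arms, and an arm-plus-PCP model is a legitimate analysis. That stands.

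Four further points also stand:
- A reader might infer that the omission widens the confidence interval. For the log odds ratio the reverse holds: adjustment raises the standard error slightly, and the odds ratio becomes conditional on the count. The gain is in power for the arm effect.
- A reader might infer that the plan states an all-patient analysis for this outcome. It does not; that is the default reading of a text naming no analysis set.
- The section 4b metrics are introduced as examples, and the definition of complex patients in section 3 also mentions medication taking. The man in step 1 may have other metrics, and the share with none at risk could be near zero. Testing and control of the same risk factor are also linked, so nine overstates the independent chances.
- A metric can become applicable during follow-up through age or a new diagnosis. Dropping patients with none at risk at baseline would discard such events, so restriction should not be the main analysis.

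The defence does not answer the central omission: exposure to the event differs between patients, can be measured at baseline, and is not used.

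**Conclusion.** The point holds as a modest efficiency gap in one of four additional assessments. Expected relative efficiency from adjusting is about 1.05–1.09, falling towards 1.0 if the number at risk varies little. This rests on assumed disease mix, gap rates, new-gap risks and PCP variation, and on the listed metrics resembling the full set.

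Two stronger conclusions are tempting and unsupported. One is that patients counted as favourable non-events distort the comparison: they dilute the risk difference in proportion to their share, but barely move the odds ratio and do not invalidate the test. The other is that this is the only measure on which worsening could appear: section 5a also records total gap counts at baseline and 6 months, which would rise if care worsened. The primary clinical outcome, closing of gaps, is not affected. The change is worth considering; the analysis is not defective without it.

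**What to change.** For this outcome only, add one linear fixed effect to the stated GLIMMIX model: the number of metrics that apply to the patient at baseline and are not already open. Keep all patients, the arm term and the PCP random effect. Report by arm how many patients had no metric at risk, and give the at-risk-only analysis as a sensitivity analysis. The same text should say what counts as a new gap and how metrics that become applicable during follow-up are treated.

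The cost is one derived baseline variable from algorithms already run for eligibility, and a sentence or two in section 5a. Because the count is fixed at baseline, the randomised comparison is preserved. The downside is a conditional odds ratio with a slightly larger standard error, which the report should state.
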